8.12.5. Kidney Biopsy

Kidney biopsies may be performed any time during the study at the discretion of the Investigator for Renal Flare or other indications.

8.12.5.1. Screening Kidney Biopsy

For participants in the LN cohort, the diagnosis of LN must have been confirmed by biopsy obtained ≤ 6 months prior to Screening or during the Screening Period.

The diagnosis of primary IgAN must have been established based on kidney biopsy obtained any time prior to or during the Screening Period.

Eligibility will be determined using the local pathology report according to standardized globally recognized guidelines. The local pathology report must be entered in the eCRF during Screening according to the CRF completion guidelines. In particular, the degree of IgG, IgA, immunoglobulin M (IgM), C3, and C1q (both cohorts); the activity score/class (LN cohort only); and the mesangial, endocapillary hypercellularity, segmental sclerosis, interstitial fibrosis/tubular atrophy-presence of crescents (MEST-C) score (IgAN cohort only), will be obtained from the local pathology reports, if available, and documented in the eCRF.

The local pathology report and microscopy slides will be sent to the Central Pathology Laboratory to confirm the diagnosis on the kidney biopsy used for eligibility to minimize interpersonal variation in histological scoring.

8.12.5.2. Kidney Biopsy During the Study

For participants in the LN cohort, a repeat biopsy at the end of the Blinded Extended Treatment Period (Week 50) will be optional and may be performed up to Week 54.

8.12.5.3. Central Pathology Laboratory

A Central Pathology Laboratory will be used to confirm the diagnosis on the kidney biopsy used for eligibility to minimize interpersonal variation in histological scoring. The Central Pathology Laboratory will be blinded to treatment allocation.

The Central Pathology Laboratory will review:

- · All kidney biopsies used for eligibility for participants in the LN cohort
- Kidney biopsies performed within 1 year of Screening or during Screening for participants in the IgAN cohort
- All kidney biopsies performed during the study any time prior to ED or completion of the Blinded Extended Treatment Period (Week 50)

The following should be sent to the Central Pathology Laboratory as soon as feasible according to the instructions in the Central Pathology Laboratory Manual:

- Copy of the local pathology report
- All light microscopy slides (hematoxylin and eosin stain [H/E], periodic acid—Schiff, Jones & Trichrome stains)
- If available, unstained microscopy slides of the kidney biopsy should also be sent to the Central Pathology Laboratory for exploratory analyses of biomarkers (Section 8.7.4). The site should send all available unstained slides, up to a maximum of 8 slides.

Every effort should be made to obtain the microscopy slides from the site pathology laboratory and ship them to the Central Pathology Laboratory. Upon confirmation with the Central Pathology Laboratory, the original biopsy slides from each participant will be returned to the study site as soon as possible. Unstained slides used for exploratory biomarker analyses will not be returned. If the shipment of microscopy slides to the Central Pathology Laboratory is prohibited due to local regulations, a slide scanner may be used to send digital images of the slides electronically, according to the instructions in the Central Pathology Laboratory Manual.

9. STATISTICAL CONSIDERATIONS

9.1. Statistical Hypotheses

The primary hypothesis for this study is that ALXN2050 180 mg bid is superior to placebo in decreasing proteinuria.

9.2. Sample Size Determination

This study plans to enroll approximately 126 adult participants with either LN or IgAN in the study (approximately 70 participants in the LN cohort and approximately 56 participants in the IgAN cohort) in a 3:1:3 ratio to ALXN2050 180 mg bid, ALXN2050 120 mg bid, or placebo. All participants will receive standard-of-care treatment in addition to their randomized treatment.

The primary analysis of the primary endpoint will test the hypothesis that ALXN2050 180 mg bid is superior to placebo in decreasing proteinuria. Data from the ALXN2050 120 mg bid treatment group will be summarized descriptively, with no formal statistical testing planned.

In March 2018, an NKF-sponsored workshop on surrogate endpoints for clinical studies in early stages of CKD was held. A 20% to 30% reduction in the geometric mean in proteinuria was decided as a clinically significant treatment effect (Levey, 2020). Sample size calculations are based on a 1-sided 2-sample t-test of log-transformed proteinuria values.

Individual patient data from relevant studies in IgAN was previously used to estimate variability and expected changes in proteinuria for patients on placebo with background standard-of-care treatment (Fellstrom, 2017). Based on this data, the geometric mean ratio (GMR) of 26-week to baseline proteinuria values is assumed to be 0.85 (ie, a 15% reduction from baseline in proteinuria) for the placebo group. In order to target at least a 30% relative treatment effect, (ie 1 minus GMR of ALXN2050 to placebo at Week 26), the GMR is assumed to be 0.55 (ie, a 45% reduction from baseline in proteinuria) for the ALXN2050 180 mg bid group. The log change from baseline in proteinuria is calculated as log (0.85) and log (0.55) for the placebo and ALXN2050 180 mg bid treatment groups, respectively, for the IgAN cohort. A common standard deviation (SD) of log change is assumed to be 0.60 (Fellstrom, 2017). Under these assumptions and an anticipated 10% drop out rate, a sample size of 48 participants (24 participants randomized to ALXN2050 180 mg bid, 24 participants randomized to placebo) in the IgAN cohort will provide approximately 80% power to detect a treatment difference with a 1-sided significance level of 0.05. An additional 8 participants will be enrolled in the ALXN2050 120 mg bid treatment group for a total of 56 participants in the IgAN cohort.

Expected changes in proteinuria and associated variability were not available on the log-scale for LN; however, 2 studies of patients with LN who were treated with MMF showed mean proteinuria values of approximately 4 g/day at baseline and approximately 2 g/day at Week 24 (Appel, 2009; Ginzler, 2005). The GMR of 26-week to baseline proteinuria values is assumed to be 0.60 (ie, a 40% reduction from baseline in proteinuria) for the placebo group. In order to target at least a 30% relative treatment effect, (ie, 1 minus GMR of ALXN2050 to placebo at Week 26), the GMR is assumed to be 0.40 (ie, a 60% reduction from baseline in proteinuria) for the ALXN2050 180 mg bid group. The log change from baseline in proteinuria is calculated as log (0.60) and log (0.40) for the placebo and ALXN2050 180 mg bid treatment groups, respectively, for the LN cohort. A common SD of log change is assumed to be 0.60

(Fellstrom, 2017). Under these assumptions and an anticipated 10% drop out rate, a sample size of 60 participants (30 participants randomized to ALXN2050 180 mg bid, 30 participants randomized to placebo) in the LN cohort will provide approximately 80% power to detect a treatment difference with a 1-sided significance level of 0.05. An additional 10 participants will be enrolled in the ALXN2050 120 mg bid treatment group for a total of 70 participants in the LN cohort.

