4.2.2. Main Analytical Approach

An analysis of covariance (ANCOVA) will be used for the primary efficacy analysis to compare reductions in proteinuria between the ALXN2050 180 mg bid treatment and placebo groups. The ANCOVA model will include change from baseline in log-transformed proteinuria as the response variable and will adjust for baseline log proteinuria and the randomization stratification factor. The treatment effect will be evaluated using the least-squares mean difference between treatment groups. The point estimate and 2-sided 90% CI for the mean difference of log-transformed proteinuria will be back transformed (via exponentiation) to obtain the geometric mean ratio (GMR) and corresponding 2-sided 90% CI. The values will then be expressed as percentage change in adjusted geometric mean of proteinuria at Week 26 relative to baseline.

The analysis will be performed for both proteinuria measures, UPCR and UP, in both cohorts even though the primary endpoint will be measured by UPCR for the LN cohort and by UP for the IgAN cohort.

The randomization stratification factor will be based on strata verified by laboratory and allowed concomitant therapy data from electronic case report form (eCRF). Sensitivity analysis may be performed using strata as randomized in the interactive response technology.

The data after the intercurrent events will be treated as missing, and all the missing data will be imputed according to the following assumptions:

In the LN cohort, only data up to the point of additional standard of care therapy will be included as observed for participants who receive additional standard of care therapy due to renal flare. Data on or after additional standard of care therapy for these participants is treated as missing regardless of whether the data is collected or not. The measurement performed at the time of renal flare (ie, proteinuria value from the 24-hour urine collection) will be carried forward to all subsequent visits.

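### The stated power of about 80% for the IgAN cohort does not survive the plan's own 10% dropout; the stated t-test then gives about 76%

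*Protocol*

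**What the plan says.** Protocol 9.2 (Sample Size Determination) sets out every input to the IgAN calculation, and SAP 5 repeats them.

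- Test: "Sample size calculations are based on a 1-sided 2-sample t-test of log-transformed proteinuria values".
- Effect: "The log change from baseline in proteinuria is calculated as log (0.85) and log (0.55) for the placebo and ALXN2050 180 mg bid treatment groups".
- Variability: "A common standard deviation (SD) of log change is assumed to be 0.60".
- Dropout and size: "Under these assumptions and an anticipated 10% drop out rate, a sample size of 48 participants", split as 24 randomized to 180 mg bid and 24 randomized to placebo.
- Result: this number "in the IgAN cohort will provide approximately 80% power to detect a treatment difference with a 1-sided significance level of 0.05".

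The LN paragraph of the same section has the same structure, with ratios of 0.60 and 0.40, the same SD and dropout, and 30 randomized per arm. It reaches the same conclusion: 60 participants "in the LN cohort will provide approximately 80% power to detect a treatment difference with a 1-sided significance level of 0.05".

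The primary analysis itself is not a t-test. SAP 4.2.2 specifies an ANCOVA that "will adjust for baseline log proteinuria and the randomization stratification factor".

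**The concern.** The IgAN sentence names dropout as one of the conditions under which the power is attained, and it describes the 24 per arm as randomized. The natural reading is that 80% is what remains after one participant in ten is lost. The stated inputs give about 80% only when all 24 per arm contribute data.

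At stake is the stated false-negative risk for the only comparison formally tested in the IgAN cohort. Protocol 9.5 says that the Week 26 analysis feeds Phase 3 planning, so anyone interpreting a non-significant IgAN result would rely on this figure.

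**Working it through.** **Inputs (Protocol 9.2 and SAP 5).** 1-sided alpha 0.05; SD of log change 0.60; ratios 0.85 (placebo) and 0.55 (180 mg bid); 24 randomized per arm; 10% dropout.

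**Effect.** Difference on the log scale = ln(0.85/0.55) = 0.4353. Geometric mean ratio = 0.55/0.85 = 0.647, a 35.3% relative reduction. Standardized effect d = 0.4353/0.60 = 0.7255.

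**Formula.** Power = P(T > t(0.95, df)), where T is noncentral t with df = n1 + n2 − 2 and noncentrality d/√(1/n1 + 1/n2). The normal approximation is Φ(noncentrality − 1.645).

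**Reproducing the stated 80%.** With 24 and 24 evaluable, df = 46, the noncentrality is 0.7255/√(2/24) = 2.513 and the critical value is 1.679. Power is 79.7% (normal approximation 80.7%). The stated figure is reproduced, but with no dropout.

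**Applying the stated 10% dropout.** 24 × 0.90 = 21.6 per arm, or 48 × 0.90 = 43.2 in total. The noncentrality at 21.6 per arm is 0.7255/√(2/21.6) = 2.384.

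| IgAN evaluable (per arm) | t-test | Normal approximation |
|---|---|---|
| 24 and 24 (no dropout) | 79.7% | 80.7% |
| 22 and 22 | 76.5% | 77.7% |
| 21.6 and 21.6 | 75.8% | 77.0% |
| 22 and 21 | 75.6% | 76.8% |

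If dropout is treated as random (binomial, 10% in each arm), the average t-test power is 75.7%. No version that applies the stated dropout reaches 78%.

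**Same check for LN.** d = ln(0.60/0.40)/0.60 = 0.6758. After dropout, 30 × 0.90 = 27 per arm.

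| LN evaluable (per arm) | t-test | Normal approximation |
|---|---|---|
| 30 and 30 (no dropout) | 82.7% | 83.5% |
| 27 and 27 | 79.0% | 79.9% |

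The LN figure agrees with 80% once dropout is applied. The IgAN figure agrees with 80% only before it is applied.

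**What 80% would take in IgAN after dropout.**

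- *Effect:* d of 0.762 to 0.769 (22 and 21.6 per arm). This is a geometric mean ratio of exp(−0.769 × 0.60) = 0.630 at 21.6 per arm, about a 37% relative reduction instead of 35.3%.
- *Variability:* an SD of 0.566 (21.6 per arm) to 0.571 (22 per arm) instead of 0.60.
- *Covariate adjustment:* a correlation of √(1 − (0.566/0.60)²) ≈ 0.33, or √(1 − (0.571/0.60)²) ≈ 0.31. The documents give no value, so this is an assumption.
- *Numbers:* 25 evaluable per arm (81.2%), which is 25/0.90 = 27.8, or 28 randomized per arm.

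**The case against.** Four points can be made for the plan.

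**The wording is approximate and the gap is small.** The word does cover LN's 79.0%. It would also cover IgAN with a single loss overall (24 and 23 evaluable: 78.9%). The shortfall is comparable to the effect of a small error in the assumed SD: at 21.6 per arm, an SD of 0.57 gives 79.5% and an SD of 0.63 gives 72.2%. This fairly limits the importance of the point. It does not make 76% a reasonable reading of a figure said to include 10% dropout when the no-dropout value is already just under 80%.

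**The planned analysis is an ANCOVA.** If the covariates had a correlation of 0.3 with the log change, power after dropout would be 79.2%; at 0.4 it would be 82.0%. These correlations are assumptions. The point stands to this extent: the 24% type II error belongs to the sizing t-test and may not be that of the primary analysis. It does not rescue the sentence, because both documents base the sample size on the t-test and neither offers a correlation or residual SD.

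**Multiple imputation keeps dropouts in the model.** The sample code in SAP 6.4.3 imputes Week 26 from treatment, baseline and stratum only. No intermediate post-baseline value enters, so imputation recovers essentially nothing beyond what the ANCOVA already uses.

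**The cause is not shown.** The documents do not display the calculation, and 24:8:24 also fits the 3:1:3 allocation neatly. An unapplied dropout allowance is the simplest explanation, but it remains an inference. The mismatch does not depend on it.

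**Conclusion.** The IgAN power statement is wrong as written. With the documents' own test, effect, SD, alpha and dropout, 24 randomized per arm gives about 76% power (75.6% to 76.5% by the t-test, 76.8% to 77.7% by the normal approximation), not about 80%. The overstatement is about 4 percentage points. The LN statement is sound.

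This rests on reading the 10% as a loss of evaluable participants spread about equally over the two arms, and on the unadjusted t-test that the documents name as the sizing method. The shortfall is modest for a Phase 2 study and does not affect the validity of the planned analysis. It is still worth correcting, because it is a headline design figure that appears in two documents.

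**What to change.** Keep the sample size. In Protocol 9.2 and SAP 5, replace the IgAN power statement with one to this effect: for the assumed ratios of 0.55 and 0.85 (a 35% relative reduction), SD 0.60 and a 1-sided 0.05 unadjusted t-test, 24 randomized per arm gives about 76% power after 10% dropout, and about 80% only if no participant is lost.

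If the sponsor prefers to keep 80%, the text should say that it relies on the ANCOVA and state the assumed correlation or residual SD, with its basis. A correlation of about 0.31 to 0.33 would be needed.

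The cost is one sentence in each of two documents. The stated IgAN figure falls by about 4 points; the LN text, the analyses and the conduct of the study are unchanged.

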9.3. Populations for Analyses

The population sets used for analysis are defined below.

Analysis Set	Description		
Enrolled Set	All consented participants excluding screen failures.		
Randomized Set	All randomized participants. Participants will be analyzed as randomized for reporting disposition, demographics, and baseline characteristics.		
Full Analysis Set (FAS)	All randomized participants who receive at least 1 dose of study intervention. Participants will be analyzed as randomized for reporting efficacy data.		
Safety Set	All participants who receive at least 1 dose of study intervention. Participants will be analyzed according to the study intervention they actually received for reporting exposure and safety data.		
Per Protocol Set	All randomized participants who receive at least 1 dose of study intervention and without important protocol deviations.		
Pharmacokinetic (PK) Analysis Set	All randomized participants who receive at least 1 dose of study intervention and who have a baseline PK value and at least 1 evaluable postdose PK assessment.		
Pharmacodynamic (PD) Analysis Set	All randomized participants who receive at least 1 dose of study intervention and who have a baseline PD value and at least 1 evaluable postdose PD assessment.		

9.4. Statistical Analyses

Statistical methods described in this section will be further elaborated in a separate Statistical Analysis Plan (SAP). The analyses for participants in the LN cohort and participants in the IgAN cohort will be conducted and reported separately.

Analyses will be performed using the SAS® software version 9.4 or higher.

9.4.1. Enrollment and Disposition

The number of participants screened, screen failed, randomized, and treated will be presented. The number of participants discontinued (along with reasons) will be summarized.

9.4.2. Demographics, Baseline Characteristics, Inclusion and Exclusion Criteria, and Protocol Deviations

All demographic information and baseline characteristics will be reported by treatment group for each disease cohort separately.

The number and percentage of participants not meeting a specific inclusion or exclusion criterion will be summarized by treatment group for each disease cohort separately. A similar summary will be provided for important protocol deviations based on prespecified categories.

9.4.3. Medical History

Medical history will be summarized using the Medical Dictionary for Regulatory Activities (MedDRA), Version 23 or later, System Organ Class (SOC) and Preferred Term by treatment group for each disease cohort separately.

9.4.4. Prior and Concomitant Medications

For analysis and reporting purposes, any medication started prior to first dose of study intervention will be considered prior medication, and medications that started on or after the first dose of study intervention will be considered concomitant medications. All prior and concomitant medications will be summarized by treatment group for each disease cohort separately.

9.4.5. Extent of Drug Exposure

The cumulative and total drug exposure and treatment duration will be summarized descriptively by treatment group for each disease cohort separately.

9.4.6. Efficacy Analyses

9.4.6.1. Analyses of Primary Efficacy Endpoint

The primary analysis of the primary efficacy endpoint will be based on the Full Analysis Set (FAS).

Proteinuria will be measured and summarized by absolute protein in g/day as well as by UPCR in g/g for each disease cohort.

For the LN cohort, the primary endpoint will be measured by UPCR in g/g derived from a single 24-hour urine collection at Screening and the mean of 2 separate 24-hour urine collections at Week 26.

For the IgAN cohort, the primary endpoint will be measured by absolute protein in g/day derived from the mean of 2 valid 24-hour urine collections.

To reduce skewness, the natural logarithm will be used to transform proteinuria values before analysis. An analysis of covariance (ANCOVA) will be used for the primary efficacy endpoint to compare reductions in proteinuria between the ALXN2050 180 mg bid and placebo treatment groups. The ANCOVA model will include change from baseline in log-transformed proteinuria as the response variable and will adjust for baseline log proteinuria. Data from the ALXN2050 120 mg bid treatment group will be summarized descriptively, with no formal statistical

comparisons planned. The point estimate and 2-sided 90% confidence interval (CI) for the mean difference of log-transformed proteinuria will be back-transformed (via exponentiation) to obtain the GMR and corresponding 2-sided 90% CI. The values will then be expressed as percentage change in adjusted geometric mean of proteinuria at Week 26 relative to baseline.

For the LN cohort, data collected on or after receipt of additional standard of care therapy will be imputed using the proteinuria value from the 24-hour urine collection performed at the time of Renal Flare for the primary efficacy analysis. Additional sensitivity analyses will be performed to assess the impact of the missing data and assumptions.

The primary efficacy endpoint analysis will also be performed on the Per Protocol Set.

Full details of these analyses will be provided in the SAP.

9.4.6.2. Analyses of Secondary Efficacy Endpoint(s)

The secondary efficacy analyses will be descriptive in nature and will be based on the FAS.

For the IgAN cohort, participants initially randomized to the placebo group will receive ALXN2050 in the Blinded Extended Treatment Period. Therefore, analysis of the secondary endpoints during the Blinded Extended Treatment Period will be summarized separately for each treatment group and baseline for the placebo group will be redefined as the last measurement taken before the first dose of ALXN2050 during the OLE Period (ie, the Week 26 measurement).

9.4.6.2.1. Secondary Efficacy Analyses for Both LN Cohort and IgAN Cohort

The percent change from baseline in proteinuria at Week 50 will be analyzed using a mixed-effect model for repeated measures (MMRM) including change from baseline in log-transformed proteinuria as the response variable and fixed, categorical effects of treatment group, visit, and treatment group by visit interaction as well as a fixed, continuous effect of baseline log proteinuria as a covariate. An unstructured covariance matrix will be used to model the correlations among repeated measurements within each participant. If this analysis fails to converge, a first-order autoregressive covariance matrix will be used. The Kenward-Roger approximation will be used to estimate denominator degrees of freedom.

- For the IgAN cohort, participants initially randomized to the placebo treatment group
 will switch to receive ALXN2050 at Week 26. Therefore, the percentage change from
 baseline in proteinuria at Week 50 will be summarized descriptively for each
 treatment group from the MMRM analysis and no formal treatment comparison will
 be made.
- For the LN cohort, the treatment effect will be evaluated for the ALXN2050 180 mg bid and placebo treatment groups using a contrast for treatment group-by-visit term at Week 50. Data from the ALXN2050 120 mg bid treatment group will be summarized descriptively, with no formal statistical comparisons planned. The point estimate and 2sided 90% CI for the mean difference of log-transformed proteinuria will be back-transformed (via exponentiation) to obtain the GMR and corresponding 2-sided 90% CI. The values will then be expressed as percentage change in adjusted geometric mean of proteinuria at Week 50 relative to baseline.

The percentage of participants with > 30% and > 50% reduction in proteinuria at Week 26 and Week 50 will be summarized by treatment group by calculating the point estimate and 2-sided 95% CI, based on exact confidence limits using the Clopper-Pearson method.

Estimated GFR will be summarized at baseline and each scheduled postbaseline time point by treatment group using descriptive statistics for the observed value as well as the change from baseline.

